43USCH2208, Clinical Investigation Plan R Lyft Chin US

Doc id

MA-52558

Effective date: 2023-05-24 22:48

Effective

Version: 4.0

SYNOPSIS

Clinical Study Title:	A randomized, evaluator-blinded, parallel group, comparator-controlled, multicenter study to evaluate the safety and effectiveness of Restylane Lyft with Lidocaine for augmentation of the chin region to improve the chin profile.
Clinical Trial Number:	43USCH2208
Country Involved and Planned Number of Study Centers:	Country: USA No of Study Centers: Approximately 12
Target Indication:	Restylane Lyft with Lidocaine is an injectable implant, intended to be used for augmentation of the chin region to improve the chin profile, in patients over the age of 21 years.
Total Number of Subjects (Planned):	Approximately 174 subjects in will be enrolled. At least 35 subjects will be Fitzpatrick skin type (FST) IV through VI, this includes at least 18 subjects with FST V – VI, where at least 9 subjects will be FST V and at least 9 subjects will be FST VI.
Clinical Study Design:	
This is a prospective, randomized, evaluator-blinded, parallel group, comparator-controlled, multicenter study in the US.
 
Approximately 174 subjects will be randomized 2:1 to treatment with either Restylane Lyft with Lidocaine (Investigational Group) or comparator, Juvéderm® Voluma™ XC (Comparator Group).
 
Injection technique is at the Treating Investigator's discretion with needle only or a combination of needle and cannula. Restylane Lyft with Lidocaine and the comparator-control will be administered by needle in the pogonion. The mentum and pre-jowl sulci may be injected by needle or cannula. After providing informed consent, eligible subjects randomized to receive either Restylane Lyft with Lidocaine or a comparator-control will be injected by the Treating Investigator at Baseline (Day 1). A follow-up telephone call should be made 72 hours after treatment and a follow-up visit should be scheduled after 14 days.
 
Optional touch-up treatment may be administered 1 month (4 weeks) after initial treatment, if deemed necessary by the Treating Investigator and the subject to obtain optimal aesthetic improvement.
 
If optional touch-up is performed, a 72-hour follow-up telephone call, a follow-up visit at 14 days and a follow-up visit at 1 month should be scheduled.
 
Investigator blinding will be accomplished by using a Treating Investigator to administer the treatments and a Blinded Evaluator, to whom randomization and treatment are concealed, to conduct the blinded assessments. Safety assessments will be performed by non-blinded personnel.
 
Effectiveness and safety data will be collected for up to 12 months (48 weeks) after last treatment including physical follow-up visits at 1, 3, 6, 9 and 12 months as well as 14 days after each treatment. A

CONFIDENTIAL

GALDERMA

G/01/19/01

Title

43USCH2208, Clinical Investigation Plan R Lyft Chin US

Doc id

MA-52558

Effective date: 2023-05-24 22:48

Effective

Version: 4.0

	
subject will be involved in the study for up to 13 months, including a 21-day screening period.
 
The study visits are illustrated in the study flow chart and the schedule of events.
 
Before study start, a randomization list will be prepared under the supervision of a designated biostatistician from the Sponsor.
 
General study safety stopping rule:
 
Enrollment and treatment in the study will be temporarily halted if a serious adverse event (SAE) occurs for the following:
 
 any unanticipated SAE which is possibly related to the study device or procedure including but not limited to a vascular embolic event that leads to skin necrosis, vision loss or stroke, damage to facial nerves which may result in facial paralysis or injury to internal facial structures. 
The SAE will be investigated by the Sponsor. If the Sponsor's investigation concludes the SAE:
 
 was unanticipated, directly related to the study product or device injection procedure, and presents an unreasonable risk to study subjects, 
the study will be terminated, and the Investigators will be notified. The institutional review board (IRB) and regulatory authority (RA) will also be notified if the study is prematurely terminated due to safety concerns. If the SAE does not meet the above criteria, then enrollment in the study will continue.

Primary Effectiveness Objective and Endpoint:	
The primary objective of the study is to demonstrate non-inferiority of Restylane Lyft with Lidocaine versus a comparator-control for augmentation of the chin region to improve the chin profile by comparing change from baseline in the Blinded Evaluator live assessment of the Galderma Chin Retrusion Scale (GCRS) at 3 months after last treatment.
 
Primary Endpoint:
 
Change from baseline in the Blinded Evaluators' live assessment using the GCRS at 3 months after last treatment.

Secondary Effectiveness Objective and Endpoints	
To evaluate the effectiveness of Restylane Lyft with Lidocaine versus a comparator-control for augmentation of the chin region to improve the chin profile, for the defined endpoints:
 
 Responder rate based on the Blinded Evaluators' live assessment using the GCRS at 3, 6, 9 and 12 months after last treatment. 
A responder is defined as a subject with at least 1 grade improvement from baseline on the GCRS.
 
CCI

CONFIDENTIAL

2023-05-24 22:48

4.0

Effective

CCI

CCI

Subgroup Analyses

To evaluate the consistency of the primary analysis results across different subgroups, specifically:

- Injection with needle
- Combination needle and cannula
- Study center

CONFIDENTIAL

GALDERMA

Title
43USCH2208, Clinical Investigation Plan R Lyft Chin US

Doc id

MA-52558

Effective date: 2023-05-24 22:48

Effective

Version: 4.0

	
 Fitzpatrick Skin Type (I–III and IV–VI) Race Ethnicity Sex at birth Age (\leq median age, and $>$ median age) Injection volume (\leq median total injection volume, and $>$ median total injection volume) 
To evaluate the consistency of AE data across different subgroups, specifically:
 
 Injection with needle Combination needle and cannula Study center Fitzpatrick Skin Type (I–III and IV–VI) Race Ethnicity Sex at birth Age (\leq median age, and $>$ median age) Injection volumes (\leq median total injection volume, and $>$ median total injection volume)
Clinical Study Duration:	
First subject first visit (FSFV) to last subject last visit (LSLV): estimated to approximately 18 months including 4 months enrollment period.
 
Duration for each Subject will be up to 14 months, including:
 
 Up to 21 days screening Treatment at Baseline (Day 1) and optional touch-up at 1 month. Data collection and safety follow-up visits at 1, 3, 6, 9 and 12 months after last treatment as well as 14 days after each treatment. 
One month is defined as 4 weeks in the study and 4 weeks is defined as 28 days.

Inclusion Criteria:	
The subjects must meet all the following criteria to be eligible for the study:
 
CCI
 
2. Males or non-pregnant, non-breastfeeding females, 22 years of age or older.
 
CCI
 
4. Intent to receive treatment for augmentation and correction of retrusion in the chin region.
 
CCI

CONFIDENTIAL

GALDERMA

Title
43USCH2208, Clinical Investigation Plan R Lyft Chin US

Doc id

MA-52558

Effective date: 2023-05-24 22:48

Effective

Version: 4.0

	
Exclusion Criteria:	
The presence of any of the following exclusion criteria excludes a subject from enrollment in the study:
 
1. Known/previous allergy or hypersensitivity to any injectable hyaluronic acid (HA) gel or to gram positive bacterial proteins.2. Known/previous allergy or hypersensitivity to local anesthetics, e.g., lidocaine or other amide-type anesthetics.3. Previous or present multiple severe allergies or severe allergies, such as manifested by anaphylaxis or angioedema, or family history of angioedema.4. Previous facial surgery (including facial aesthetic surgery and liposuction) below the level of the horizontal line from the subnasale.5. Any previous aesthetic procedures or implants: 

GALDERMA

Title
43USCH2208, Clinical Investigation Plan R Lyft Chin US

Doc id

MA-52558

Effective date: 2023-05-24 22:48

Effective

Version: 4.0

- Previous mechanical (e.g., dermabrasion, needling) or chemical aesthetic procedures (e.g., medical chemical peel, mesotherapy) below the level of the horizontal line from subnasale within 6 months.
- Previous cryolipolysis treatment below the level of the horizontal line from subnasale within 6 months.
- Oral surgery (e.g., tooth extractions, orthodontia, or implantation) within 6 months.

CCI

7. Presence of any disease or lesions near or on the area to be treated, e.g.,

- Inflammation, active or chronic infection (e.g., in mouth, dentals, head and neck region).
- Facial psoriasis, eczema, acne (defined as active inflammatory reaction), rosacea, perioral dermatitis, herpes simplex or herpes zoster.
- Scars or deformities.
- Cancer, or precancer such as actinic keratosis or actinic cheilitis.

CCI

CONFIDENTIAL

GALDERMA

(S/N: 1581)

[figure not shown]
Title
43USCH2208, Clinical Investigation Plan R Lyft Chin US

Doc id
MA-52558

Effective date: 2023-05-24 22:48

Effective

Version: 4.0

CONFIDENTIAL

GALDERMA

G.D. 1981

Title

43USCH2208, Clinical Investigation Plan R Lyft Chin US

Doc id

MA-52558

Effective date: 2023-05-24 22:48

Effective

Version: 4.0

Investigational Product:	Restylane Lyft with Lidocaine is a sterile gel of HA generated by Streptococcus species of bacteria, chemically cross-linked with BDDE, stabilized and suspended in phosphate buffered saline at pH=7 and concentration of 20 mg/mL with 0.3% lidocaine.
Comparator/Placebo Product:	Juvéderm Voluma XC is a sterile gel of HA produced by the Streptococcus species of bacteria, which is crosslinked with BDDE. It is formulated to a concentration of 20 mg/mL and 0.3% w/w lidocaine in a physiologic buffer.
Treatment area:	The treatment area includes the chin and surrounding regions: pogonion, mentum and pre-jowl sulci. Subjects will be treated to optimal chin retrusion correction, which is defined as at least 1 GCRS grade improvement from Baseline and best correction that can be achieved as agreed upon by the Treating Investigator and the subject.
Treatment regimen:	Subjects in the treatment group will receive injection in the chin and surrounding regions with either Restylane Lyft with Lidocaine or a comparator-control at Baseline (initial treatment) with optional touch-up treatment 1 month (4 weeks) after initial treatment, if deemed necessary by Treating Investigator and subject to obtain optimal aesthetic improvement.
Mode of administration:	Injection technique is at the Treating Investigator's discretion (with needle only or a combination of needle and cannula). Injection should be in the deep subcutaneous tissue or supraperiosteal plane, as per Investigator's discretion. Appropriate injection volume for the chin area will be determined by the Treating Investigator but is not to exceed a maximum total volume of 4.0 mL for initial and touch-up treatments combined. Injection in the pogonion is only permitted with a needle; a cannula is permitted for injection in the other treatment areas. Depending on the location, serial puncture and linear threading among other techniques can be used to safely and effectively enhance the contour, shape and definition of this aesthetic region. The injection method and depth of injection, number of syringes used, and the volume of study product injected during each injection session will be recorded in the electronic Case Report Form (eCRF). Aspiration is recommended prior to each injection. Slow injection is recommended, and overcorrection should be avoided.
Statistical Method:	In general, all effectiveness, safety and baseline characteristics variables will be presented using descriptive statistics and graphs as appropriate. Continuous endpoints will be summarized using descriptive statistics, e.g., mean, median, standard deviation, minimum and maximum values. Categorical endpoints will be presented in frequency tables with number and percentage of observations for each level. The primary effectiveness analysis is test of non-inferiority of Restylane Lyft with Lidocaine to a comparator-control Juvéderm Voluma XC in the Intention to treat (ITT) and Per Protocol (PP) analysis sets, using the confidence interval (CI) approach and non-inferiority margin of 0.5 units. The change from baseline in GCRS, as assessed by the Blinded Evaluator, will be analyzed using a mixed effect model with treatment as fixed effect and subject as random factor. The change from baseline at Month 3, after last treatment, will be the response variable. Non-inferiority will be established if the upper limit of the confidence interval (CI) is below

CONFIDENTIAL

GALDERMA

Title
43USCH2208, Clinical Investigation Plan R Lyft Chin US

Doc id
MA-52558

Effective date: 2023-05-24 22:48

Effective

Version: 4.0

the non-inferiority margin of 0.5 units. Superiority will be declared if the upper limit is below 0. This decision criterion is consistent with a gate-keeping strategy (testing for superiority following the test for non-inferiority) to maintain the overall type I error rate at 2.5%.

Secondary analyses

For the GCRS, a responder will be defined as a subject with at least 1 point improvement from baseline based on the GCRS. For a significant result, the two-sided p-value of the comparison of responder rates between the treatment groups at Month 3, 6, 9 and 12 using the Fisher's exact test. The estimates of the responder rate in each treatment group will be presented with corresponding CIs.

CCI

CONFIDENTIAL

GALDERMA

Title
43USCH2208, Clinical Investigation Plan R Lyft Chin US

Doc id

MA-52558

Effective date: 2023-05-24 22:48

Effective

Version: 4.0

	
Sample Size:	
Approximately 174 subjects will be treated in the study, randomized in a 2:1 ratio (116 with Restylane Lyft with Lidocaine; 58 with Juvéderm Voluma XC).
 
For sample size calculation of 174, it was assumed that the true effectiveness of Restylane Lyft with Lidocaine compared to control treatment assessed by the GCRS is approximately 0.1 point lower. A common standard deviation of 0.7 point was assumed for the treatments. Based on the non-inferiority margin of 0.5, a total sample size of 147 evaluable subjects is then required to show non-inferiority of Restylane Lyft with Lidocaine to the control treatment with a power of 90%, using a two-sided 95% CI for the difference between treatment means.
 
Accounting for approximately 15% dropouts and non-evaluable subjects due to protocol deviations at 3 months, a total of approximately 174 subjects will be randomized in the study.

Interim Analysis:	No interim analysis is planned.
Effectiveness Assessments	
 • Blinded Evaluator GCRS • Treating Investigator GCRS 
Safety Assessments	
 1. Adverse Event reporting: AEs will be obtained from signs and symptoms reported by the Subject or detected during each examination. Any ongoing AEs related to product or injection procedure will be followed until resolved or chronic/stable through end of study participation. 2. A subject diary will be dispensed to all subjects for daily completion over the first 28 days after each treatment to record the following pre-identified symptoms: bruising, redness, tenderness, swelling, pain, lumps/bumps, itching, and other. Subjects will be specifically asked to record any of the following symptoms in the other section; changes in vision (i.e., loss of vision, blurriness, double vision, pain in

CONFIDENTIAL

GALDERMA

G.D. 1981

Title

43USCH2208, Clinical Investigation Plan R Lyft Chin US

Doc id

MA-52558

Effective date: 2023-05-24 22:48

Effective

[figure not shown]
Version: 4.0

	
or around your eye, blindness, blind spots, problems moving your eyes), skin changing color around the eyelids, crusty or scabby skin around the eyelids, pain, headache, fever, dizziness, confusion, weakness or numbness in the arms or legs, changes to consciousness or alertness, difficulty speaking/speech impairment and face droop, changes in ability to chew and drink, sensitivity to hot and cold or subject discomfort. Information from the diary will be presented separately from other AEs.
 
 • Contact the study doctor immediately if they experience severe pain, headache, fever, skin changing color near the injection site, or crusty or scabby skin near the injection site. • Contact an eye doctor (retinal specialist or ophthalmologist) if they experience changes in vision (i.e., vision loss, blurriness, double vision, pain in or around eye, blindness, blind spots, problems moving your eyes), change in skin color, or crusty/scabby skin around the eyelids. • Call 911 and seek immediate medical attention if signs of stroke or subject experience dizziness, confusion, weakness, or numbness in face, arms or legs, changes to consciousness or alertness, difficulty speaking/speech impairment, or face droop. 
 3. Visual function assessments (i.e., Snellen visual acuity test, extraocular muscle function test, and confrontation visual field test) at baseline and at all following physical visits. At treatment visits, the assessments will be performed both prior to and post injection of the study product. 4. Subject pain assessment before (prior to application of any anesthetic) and immediately after (before any post-injection therapy is provided, e.g., ice packs) treatment, using an 11-point Numeric Pain Scale (NPS). 5. Changes in hair growth (e.g., loss or growth) in the treated area, at each physical follow-up visit after baseline. 6. Lower lip movement, chin and lip function and sensation, according to pre-defined methods, at baseline and at each physical follow-up visit. 7. Palpation tests according to pre-defined methods, at screening, baseline and at each physical follow-up visit. 8. Device deficiencies will be assessed at treatment visits.
--	---

CONFIDENTIAL

CLINICAL STUDY FLOW CHART

Figure 1 Study Flow Chart

GALDERMA

Title
43USCH2208, Clinical Investigation Plan R Lyft Chin US

Doc id

MA-52558

Effective date: 2023-05-24 22:48

Effective

Version: 4.0

ABBREVIATIONS AND DEFINITIONS OF TERMS

AE	Adverse Event
AESI	Adverse event of special interest
BDDE	1,4-butanediol diglycidylether
BOCF	Baseline observation carried forward
CFR	Code of Federal Regulations
CI	Confidence interval
CMC	Chemistry, manufacturing and control
COX-2	Cyclooxygenase-2
CRO	Contract Research Organization
CSP	Clinical Study Protocol
CSR	Clinical Study Report
CTA	Clinical Trial Agreement
CTN	Clinical Trial Number
CV	Curriculum vitae
DMP	Data Management Plan
eCRF	Electronic case report form
EOS	End of study
FDA	Food and Drug Administration
FSFV	First subject first visit
FST	Fitzpatrick Skin Type
CCI	
GCP	Good Clinical Practice
GCRS	Galderma Chin Retrusion Scale
GDPR	General Data Protection Regulation
GLP	Good laboratory practice
HA	Hyaluronic acid
HIPAA	Health Insurance Portability and Accountability Act of 1996
HIV	Human immunodeficiency virus
ICF	Informed Consent Form
ICH	International Conference on Harmonisation
IFU	Instructions for Use
CCI	
IRB	Institutional review board
ITT	Intention to treat
IUD	Intra uterine device
LSLV	Last subject last visit
MedDRA	Medical Dictionary for Regulatory Activities
MDR	Medical Devices Regulation
MI	Multiple imputation
n	Number of subjects
NPS	Numeric Pain Scale
NSAID	Non-steroidal anti-inflammatory drugs
PI	Principal Investigator
PP	Per protocol
PMS	Post market surveillance
PT	Preferred term
RA	Regulatory Authority
ROPI	Report of prior investigations

CONFIDENTIAL

GALDERMA

6301135801

Title
43USCH2208, Clinical Investigation Plan R Lyft Chin US

Doc id

MA-52558

Effective date: 2023-05-24 22:48

SAE	Serious Adverse Event
SAP	Statistical Analysis Plan
SD	Standard deviation
SDV	Source Data Verification
SOC	System organ class
CCI	
TC	Telephone call
Tx	Treatment
UADE	Unanticipated adverse device effect
UPT	Urine pregnancy test
UTW	Ultra-thin wall
WHO	World Health Organization

Effective

Version: 4.0

CONFIDENTIAL

Effective date: 2023-05-24 22:48

Effective

Version: 4.0

Table of Contents

TITLE PAGE	2
INVESTIGATORS AND STUDY ADMINISTRATIVE STRUCTURE	3
SYNOPSIS	4
CLINICAL STUDY FLOW CHART	15
SCHEDULE OF EVENTS	16
ABBREVIATIONS AND DEFINITIONS OF TERMS	18
1. BACKGROUND INFORMATION	25
1.1 Medical background, indication, and population description	25
1.2 Relevant previous data	25
1.2.1 Non-clinical documentation	25
1.2.2 Clinical documentation	25
1.3 Risks and benefits	26
2. STUDY OBJECTIVES, ENDPOINTS AND HYPOTHESIS	26
2.1 Study objectives	26
2.1.1 Primary objective and endpoint	26

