5.3 Instructions for use and administration

The study product is reserved for use by Treating Investigators who are experienced in chin area procedures. Treating Investigators should be aware of important neurovascular and anatomical structures near the injection site. The Treating Investigator must be trained on, and have at hand, the relevant clinical practice guidelines¹ and the actions to be taken if visual disturbances occur. The Treating Investigator should also have reviewed the Intravascular Treatment Protocol supportive tool provided separately in the Investigator file.

Detailed information regarding the injection procedure, pre- and post-treatment care and subjects' instructions are provided in the respective IFUs for *Restylane Lyft with Lidocaine* (study specific IFU) and *Juvéderm Voluma XC* (commercially available IFU).

Please also refer to the ROPI for *Restylane Lyft with Lidocaine* for a description of performed clinical studies, PMS data on reported AEs, and published data related to injections of HA in the chin area.

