5.3.1 Pre-treatment procedure

Before treatment, the subject will be informed about expected post-treatment events that should be recorded in the Subject Diary, if experienced, potential risks involved with the treatment, and when to contact the Investigator in case of emerging symptoms.

It is necessary to counsel the subject and discuss the appropriate indication, risks, benefits, and expected responses to the *Restylane Lyft with Lidocaine* and *Juvéderm Voluma XC* treatment.

- Advise the subject of the necessary precautions before commencing the procedure.

Prior to treatment, the subject's medical history should be obtained, and the s/he should be fully appraised of the indications, contraindications, warnings, precautions, treatment responses, adverse reactions, and method of administration. Subjects also should be advised that supplemental touch-up implantations may be required to achieve and maintain the desired level of correction.

Prohibited concomitant medication use should be checked before any treatment is given (see Section 4.3.4).

CONFIDENTIAL

Effective date: 2023-05-24 22:48

Effective

Version: 4.0

For subjects who have experienced medically important AEs during initial treatment, a decision for touch-up should take into consideration the cause and severity of previous reactions.

Subjects need for appropriate anesthetic treatment for managing comfort, i.e., topical anesthetic, local or nerve block should be assessed. If the treated area is swollen directly after the injection, an ice pack can be applied on the site for a short period. Ice should be used with caution if the area is still numb from anesthetic to avoid thermal injury.

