5.3.3 Post-treatment care

When the injection is completed, the treated area may be gently molded or massaged to avoid any irregularities.

Brisk molding or massaging should be avoided in order to prevent undue swelling of the region.

Post treatment procedures with ice pack is allowed as per investigator normal procedure. Ice pack can be applied for a short period if the treated area is swollen.

After the injection, some common injection-related reactions might occur. These reactions include redness, swelling, pain, itching, bruising or tenderness at the implant site. Typically, resolution is spontaneous within two to four weeks after injection into the skin.

Any medication or therapy used by the subject must be recorded in the eCRF.

Subjects will be asked to:

- Avoid heat (sunbathing, sauna, steam baths, etc.) or extreme temperatures until any signs of local inflammation have disappeared.

GALDERMA

Title
43USCH2208, Clinical Investigation Plan R Lyft Chin US

Doc id

MA-52558

Effective date: 2023-05-24 22:48

- Avoid touching or shaving the treated area and not to apply any creams or cosmetics in the treated area before the skin has healed completely in order to prevent infections or elicit an inflammatory reaction.
- Abstain from prohibited medications, treatments and procedures (see Section 4.3.4).
- Contact the study center if common injection-related reactions such as bruising, redness, pain, tenderness, lumps/bumps, itching, swelling at the injection site, have not diminished within two weeks or if they get worse.
- Contact the study center if they have signs of infection and/or inflammation such as pain, tenderness, heat, redness, swelling, small lumps that contain pus or yellowish fluid, and fever. These symptoms can occur within days or several weeks after treatment.

Subjects treated with the comparator *Juvéderm Voluma XC*, should also avoid strenuous exercise within the first 24 hours of treatment. Please refer to post-treatment recommendation in the IFU provided with the product.

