7.6 Visual function assessment

Visual function assessments will be performed at screening, baseline and at all physical follow-up visits. At the treatment visits, the visual function assessment tests will be performed prior to and approximately 30 minutes post injection of the study product. These assessments include Snellen visual acuity, extraocular muscle function, and confrontation visual field tests.

The subject is considered to have normal or acceptable visual acuity if the Investigator can adequately measure the quality of his/her eyesight using the Snellen Eye Chart. If the subject is found to have severely impaired/absent eye function (20/50 or worse) in one or both eyes, even with the use of prescribed corrective lenses, and/or any other condition with the potential to cause a decline of visual acuity, s/he will be considered to have abnormal vision and will not be eligible for enrollment.

All worsening of vision during the study (for visual acuity compared to baseline and post injection compared to pre injection at treatment visits) should be assessed by the Investigator **as an adverse event of special interest (AESI)** per Section 7.10. If the subject experiences clinically significant changes in vision, the Investigator should consider further assessment and treatment by an eye specialist (ophthalmologist or retinal specialist). The Investigator should conduct appropriate follow-up with the subject to determine the cause, intensity, seriousness, relationship to the study product or procedures, and outcome.

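### The Synopsis instruction sending subjects with vision changes to an eye doctor carries no word of urgency, unlike the two instructions beside it; one added word would fix this.

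*Protocol*

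**What the plan says.** The Synopsis, under Safety Assessments, follows its description of the subject diary with three contact instructions:

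- "Contact the study doctor immediately if they experience severe pain, headache, fever", extended to skin colour change or crusting near the injection site.
- "Contact an eye doctor (retinal specialist or ophthalmologist) if they experience changes in vision", with a list that runs from blurriness and double vision to vision loss and blindness, and then adds skin changes around the eyelids.
- "Call 911 and seek immediate medical attention if signs of stroke", followed by a list of neurological symptoms.

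Other parts of the protocol bear on what subjects are told and what the site does. Section 5.3.1 requires that subjects be told before treatment "when to contact the Investigator in case of emerging symptoms". The contact list in 5.3.3 covers common injection reactions that persist or worsen, and "Contact the study center if they have signs of infection and/or inflammation"; it names neither vision nor stroke symptoms. Section 5.3 requires the Treating Investigator to be trained on "the actions to be taken if visual disturbances occur" and says of the injection procedure, care and subject guidance that detailed "instructions are provided in the respective IFUs". Section 7.6 says that, for clinically significant changes in vision, "the Investigator should consider further assessment and treatment by an eye specialist (ophthalmologist or retinal specialist".

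**The concern.** The three instructions stand together as a short list of what to do in an emergency. Two of them say how fast to act. The one covering possible loss of sight does not, so a subject or site relying on this wording could take it to mean that an ordinary eye appointment will do.

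The rest of the protocol does not treat vision loss that way. Section 1.2.2 asks the treating physician for prompt medical attention in intravascular or embolic events. Section 7.10 makes all visual disturbances adverse events of special interest, whatever their cause or seriousness. Section 7.14 names an embolic event leading to vision loss among the unanticipated, possibly related serious events that temporarily halt enrollment and treatment. The stake is the safety of the individual subject. Nothing in the effectiveness analysis depends on it.

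**Working it through.** No arithmetic applies. The check is a side-by-side reading of the visible Synopsis text, followed by a search for the same instruction elsewhere in the protocol.

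| Trigger | Whom to contact | Time word |
|---|---|---|
| Severe pain, headache, fever, skin change near the injection site | Study doctor | 'immediately' |
| Vision changes, including vision loss and blindness; skin change around the eyelids | Eye doctor | none |
| Stroke signs and related neurological symptoms | 911 and medical care | 'immediate' |

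**Step 1: is the vision bullet complete?** Yes. It is visible from start to end with no blacked-out gap, so the missing time word does not come from redaction of that sentence.

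**Step 2: does the lack of urgency look deliberate?** Nothing in the text says so. Skin colour change or crusting appears in both of the first two bullets, near the injection site in one and around the eyelids in the other. It carries a time word only in the first. No reason is given for the difference.

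**Step 3: is urgency supplied elsewhere in the visible text addressed to subjects?** Section 5.3.3 does not mention vision. Section 5.3.1 requires counselling on when to contact the Investigator, but names no symptom and gives no time. Sections 1.2.2, 5.3 and 7.6 are addressed to the physician, not the subject.

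**Step 4: what cannot be seen?** Section 7.7 is blacked out and is probably the diary section. The other safety assessments in the Synopsis have their own places: pain 7.1, sensation 7.2, function 7.3, palpability 7.4, hair growth 7.5, vision 7.6, adverse events 7.9 and device deficiencies 7.12. The diary has none, and 7.7 is the open slot between vision and pregnancy testing. The SAP points the same way: its contents page lists subject diary data in the title of section 4.5.1, and that part of the title is blacked out in the body. The diary itself, the consent form and the instructions for use are not in the file.

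**Result.** The missing urgency word in the visible vision bullet is established. What the subject-facing documents say is unknown.

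**The case against.** The strongest reply is that a synopsis is a summary, not the text handed to subjects. The three bullets have no lead-in sentence and read as condensed. Fuller wording may well stand in section 7.7, the diary, the consent form or the instructions for use, and text that is redacted or outside the file cannot be counted as absent from the plan. This stands as a limit on the conclusion. It does not answer the narrow point: the visible bullet is complete and weaker than its neighbours, and bringing it into line is worthwhile even if better wording exists elsewhere.

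A second reply is that the bullets sort symptoms by type of care: study doctor, eye specialist, emergency services. Direct access to a retinal specialist or ophthalmologist is not a lower tier. This also stands. A reader might infer that the protocol ranks fever above blindness. The documents do not support that, because the bullets differ in destination as well as in timing, and each covers a mix of milder and graver symptoms.

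A reader might also infer that the site is left uninformed, because neither the vision nor the stroke bullet mentions it. That is not shown. Section 5.3.1 requires counselling on contacting the Investigator and excludes no symptom. Vision and stroke-type symptoms are to be recorded in the diary, which the site reviews. The 72-hour calls ask about adverse events and send any report to the Investigator at once (8.3.1, 8.3.4). Section 7.13 also accepts spontaneous reports from subjects or relatives. No reporting rule is breached either, since the 24-hour clock in 7.13.1 runs from awareness.

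**Conclusion.** The point holds in its narrow form. In the visible Synopsis instructions, the bullet for vision changes, including loss of sight, lacks the word of urgency that the other two carry, and this fits poorly with how sections 1.2.2, 7.10 and 7.14 treat such events. It is an optional, low-severity improvement in wording. It has no effect on the primary endpoint, sample size, analysis or error rate.

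No frequency or length of delay can be given, because the documents do not show how often a subject would act late on this wording. The intervals between scheduled visits would not serve as an estimate: they are not expected delays, and the longer ones fall largely outside the 28-day diary period to which these instructions belong.

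The conclusion rests on the Synopsis text alone. If the diary, consent form and study-specific instructions for use already say to act at once, the remaining issue is consistency between documents.

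**What to change.** In the Synopsis vision bullet, insert 'immediately' after the words naming the eye doctor, and add the clause 'and inform the study doctor as soon as possible'. The first change is the substantive one. The second is a consistency addition: it matches the Investigator's role in sections 5.3 and 7.6 but does not repair a proven gap.

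Then check that the diary, the consent form and the study-specific instructions for use say the same, and correct any that do not. The comparator's instructions for use are the commercial ones from its manufacturer, so subjects in that arm should be covered through the diary and consent form.

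The cost is one word and one clause in the Synopsis plus a document check. It can wait for the next amendment, which needs IRB approval in any case (10.7); a change to the consent form also needs IRB approval (10.2). The downside is a few more urgent contacts with eye doctors and sites for minor visual symptoms.
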